6.7.2 Adverse Events

Summaries of unsolicited adverse events are described in section 6.7.1

6.7.3 Other Safety parameters

Body weight and temperature, recorded prior to vaccination, will be provided as a by-subject listing.

Physical Examination Findings will be provided as a by-subject listing.

6.7.4 Subgroup Analysis

The safety analyses for QIVc and comparator vaccine will be performed by stratifying for the following subgroups:

- Subjects aged “6 through 23 months” and “24 through 47 months”.

Statistical Analysis Plan – Final v2.0

Sponsor Name: Seqirus UK Limited
Sponsor Protocol ID: V130_14

- Subjects “previously vaccinated” and “not-previously vaccinated”.
- Subjects by race.
- Subjects by gender.
- Subjects by country or region.
- Subjects by season/year treated.

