### **8.3.7 Subgroups**

The efficacy analyses will be performed by stratifying for the following subgroups:

- Subjects aged “6 through 23 months” and “24 through 47 months”.
- Subjects “previously influenza vaccinated” and “not-previously influenza vaccinated”.
- Subjects by race.

- Subjects by sex.
- Subjects by country or region.
- Subjects by season/year treated.

The immunogenicity analyses will be performed by stratifying for the following subgroups:

- Subjects aged “6 through 23 months” and “24 through 47 months”.
- Subjects with pre-vaccination HI (or MN) titer <1:10 and pre-vaccination HI (or MN) titer  $\geq$  1:10.
- Subjects “previously influenza vaccinated” and “not-previously influenza vaccinated”.
- Subjects by race.
- Subjects by sex.
- Subjects by country or region.
- Subjects by season/year treated.

The safety analyses will be performed by stratifying for the following subgroups:

- Subjects aged “6 through 23 months” and “24 through 47 months”.
- Subjects “previously vaccinated” and “not-previously vaccinated”.
- Subjects by comparator (MenC or saline for injection).
- Subjects by race.
- Subjects by sex.
- Subjects by country or region.
- Subjects by season/year treated.

Safety and immunogenicity analyses will also be performed by time periods as detailed in SAP. Any other additional analyses may be performed, as described in Statistical Analysis Plan (SAP).

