2.2 Overall Study Design

This multicenter phase III clinical study evaluates the efficacy, immunogenicity and safety of a cell-based quadrivalent subunit influenza virus-vaccine compared to non-influenza vaccine in subjects between 6 months through 47 months of age. The study features an observer blind design, parallel groups and 1:1 randomization between QIVc and a non-influenza vaccine (Meningococcal Group C Polysaccharide Conjugate Vaccine (MenC-vaccine)).

Based on previous influenza vaccination history, subjects will receive either one or two doses of either QIVc or comparator (non-influenza vaccine/placebo).

The study is designed to accrue an approximate number of subjects and a minimum number of cases over several influenza seasons. Each subject will participate until the end of the influenza season as defined in the protocol for the season in which the subject is enrolled but at least 180 days after last vaccination in the treatment period (defined below).

The study has a treatment period and a follow-up period.

For subjects with a previous influenza vaccination history (named also “previously vaccinated” subjects in the document):

- The treatment period begins at the time of vaccination (Day 1) and ends 28 days after vaccination (Day 29) and will consist of 2 clinical visits and one reminder call to complete the Subject diary card.
- The follow up period begins 28 days after vaccination and ends at the time of study completion visit.

For subjects without or unknown previous influenza vaccination history (named also “not previously vaccinated” subjects in the document):

- The treatment period begins at the time of first vaccination (Day 1) and ends 28 days after the second vaccination (Day 57) and will consist of 3 clinical visits and two reminder calls to complete the Subject diary card, one after each vaccination.

Statistical Analysis Plan – Final v2.0

Sponsor Name: Seqirus UK Limited
Sponsor Protocol ID: V130_14

- The follow-up period begins 28 days after second vaccination and ends at the time of study completion visit.

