All subjects, irrespective of previous influenza vaccination history, will receive 1 safety follow-up call 90 days after last vaccination during the follow up period and the follow-up period will conclude with a study completion visit (clinic visit or call). All subjects aged 6 through 11 months at enrollment, irrespective of randomization to investigational or comparator group, will receive a dose of the MenC vaccine at the end of the study.

The timing and frequency of the study visits are described in Schedule of Assessments ([Appendix A](#)).

The treatment arms of Study Vaccine comprise:

Study treatment:

Subjects who meet the entry criteria will be stratified by age and vaccination history and then randomized to one of the two treatment groups using a 1:1 allocation ratio to receive either Seqirus QIVc or the MenC-vaccine.

Investigational treatment

A cell-derived quadrivalent inactivated subunit influenza vaccine (QIVc) will be used as investigational vaccine.

Vaccination schedule:

- Subjects ≥ 12 months with a previous influenza vaccination history: One dose of QIVc at Visit 1.
- Subjects ≥ 12 months without a previous influenza vaccination history and subjects 6 through 11 months: One dose of QIVc at Visit 1 followed by one dose of QIVc at Visit 2.

Comparator treatment:

Meningococcal Group C Polysaccharide Conjugate Vaccine (MenC vaccine, Neisvac-C, Pfizer) will be used as a comparator.

Vaccination schedule:

- Subjects ≥ 12 months with a previous influenza vaccination history: One dose of MenC vaccine at Visit 1.
- Subjects ≥ 12 months without a previous influenza vaccination history and subjects 6 through 11 months: One dose of MenC vaccine at Visit 1 followed by one dose of placebo (saline for injection) at Visit 2.
- All subjects aged 6 through 11 months at enrollment, regardless of treatment assignment, will receive a dose of the MenC vaccine at Visit 5.

Statistical Analysis Plan – Final v2.0

Sponsor Name: Seqirus UK Limited
Sponsor Protocol ID: V130_14

Withdrawn Subjects

Subjects may withdraw from the study at any time at their own request or request of the parent or legally appropriate representative, or they may be withdrawn at any time at the discretion of the investigator should any untoward effects occur and/or for safety reasons.

The reasons for premature withdrawal from the study include the following:

- Adverse event (AE)
- Death
- Withdrawal of consent
- Lost to follow-up
- Other
- Protocol deviation

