3.2 Secondary Safety Endpoints

The measures for assessing safety and tolerability are as follows:

1. Percentage of subjects with solicited local and systemic AEs will be assessed for 7 days following each vaccination in the QIVc group and the comparator group.
2. Percentage of subjects with any unsolicited AEs will be assessed in the QIVc group and in the comparator group until 28 days after each vaccination.
3. Percentage of subjects with Serious Adverse Events (SAEs), New Onset of Chronic Diseases (NOCDs), AEs leading to withdrawal from the study or vaccination, and all medications associated with these events will be reported in the QIVc group and in the comparator group.
4. Percentage of subjects with medically-attended AEs within 30 days after ILI onset will be reported in the QIVc group and in the comparator group.

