The original verbatim terms used by investigators to identify AEs in the CRFs will be mapped to preferred terms using the Medical Dictionary for Regulatory Activities (MedDRA) dictionary. The AEs will then be grouped by MedDRA preferred terms into frequency tables according to SOC. All reported AEs, as well as AEs judged by the investigator as at least possibly related to study vaccine, will be summarized presenting the number and percentage of subjects having one or more events according to system organ class and preferred term within system organ class. These summaries will be presented by vaccination group and period (as defined in section 2.2): treatment period, follow up period and total observation period (Day 1 until study end). When an AE occurs more than once for a subject, the maximal severity and strongest relationship to the vaccine group will be counted.

Separate summaries will be produced for the following categories:

- SAE
- NOCD
- Adverse events/Serious Adverse events that are possibly or probably related to vaccine
- Adverse event leading to study withdrawal or early termination
- Adverse events leading to a medically-attended visit within 30 days after the onset of ILI episode
- Adverse events leading to a medically-attended visit during the treatment period
- Adverse event resulting in death

Data listings of all adverse events will be provided by subject. In addition, adverse events in the categories above will be provided as listed data.

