For the interim analyses, a restricted unblinding will be done, i.e., only DMC members and unblinded CRO employees responsible for the analyses will receive access to the randomization codes and unblinded data for the purpose of preparing the interim analyses (further information on handling of the blinding for the interim analyses can be found in protocol section 3.3). The results of the interim analyses are only for DMC purposes and will not be reported in the CSR.

7 Changes in Planned Analysis

The term 'sex' has been replaced with 'gender' throughout the analysis section. The definition of FAS Overall has been added to this SAP for baseline and background data description purpose.

8 Data Issues

Not applicable.

9 References

- 1 ICH. *Statistical Principles for Clinical Trials*, Guideline E9, 1998. Available at <http://www.emea.eu.int/pdfs/human/ich/036396en.pdf>
- 2 CPMP. *Points to Consider on Missing Data*. EMEA: London, 2001. Available at <http://www.emea.eu.int/pdfs/human/ewp/177699EN.pdf>
- 3 Phillips A and Haudiquet V. *ICH E9 guideline "Statistical principles for clinical trials": a case study*. Statistics in Medicine 2003; 22:1-11
- 4 Brown D J. *ICH E9 guideline "Statistical principles for clinical trials": a case study. Response to A. Phillips and V. Haudiquet*. Statistics in Medicine 2003; 22:13-17
- 6 Senn S. *Statistical Issues in Drug Development*. John Wiley & sons (Chichester), 1997.
- 7 Chow S-C and Liu J-P. *Design and Analysis of Clinical Trials: Concepts and Methodologies*. John Wiley & sons (New York), 1998.
- 8 Brown H and Prescott R. *Applied Mixed Models in Medicine*. John Wiley & sons (Chichester), 1999.
- 9 Fairclough D L. *Design and Analysis of Quality of Life Studies in Clinical Trials*. Chapman & Hall/CRC, 2002.
- 10 Green S, Benedetti J and Crowley J. *Clinical Trials in Oncology (2nd edition)*. Chapman & Hall/CRC, 2002.
- 11 McEntegart D. *Forced randomization when using interactive voice response systems*. Applied Clinical Trials October 2003; 50-58.
- 12 CPMP. *Points to Consider on Adjustment for Baseline Covariates*. EMEA: London, 2003

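### SAP 6.7.4 drops the protocol's safety split by comparator without declaring it, and no planned unsolicited-AE table separates saline from MenC

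*SAP*

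**What the plan says.** Protocol 8.3.7 lists seven safety subgroups: age, vaccination history, comparator, race, sex, country or region, and season. The comparator item reads "Subjects by comparator (MenC or saline for injection").

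SAP 6.7.4 introduces its own list with "The safety analyses for QIVc and comparator vaccine will be performed by stratifying for the following subgroups". It repeats age, vaccination history, race, gender, country or region, and season. The comparator item is absent. SAP section 7, which records changes from the protocol, mentions the move from sex to gender and adds "The definition of FAS Overall has been added to this SAP for baseline and background data description purpose". It does not mention the comparator split.

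For not-previously vaccinated comparator children, SAP 2.2 specifies "One dose of MenC vaccine at Visit 1 followed by one dose of placebo (saline for injection) at Visit 2". QIVc children on the same schedule receive QIVc twice.

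For unsolicited AEs, including those judged related, SAP 6.7.1.3 says: "These summaries will be presented by vaccination group and period (as defined in section 2.2): treatment period, follow up period and total observation period". SAP 2.2 runs the treatment period of two-dose children from Day 1 to Day 57, so it spans both doses. The same section plans a summary of medically-attended AEs in the treatment period.

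Solicited AEs are handled differently: SAP 4.3 divides the Solicited Safety Set into after vaccination 1, after vaccination 2, and overall.

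**The concern.** A safety analysis listed in the protocol is missing from the SAP with no stated reason, and for unsolicited AEs nothing else in the SAP takes its place. In two-dose comparator children, the treatment-period percentage counts a child once for an event after MenC, after saline, or after both. MenC is an aluminium-adsorbed conjugate vaccine; saline is a masking dose. The QIVc-versus-comparator difference in that table therefore depends partly on how reactive MenC is, and a reader cannot recover how QIVc compares with an inert injection.

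All children aged 6 through 11 months are on the two-dose schedule, so the youngest participants are always in the affected group. At stake is the interpretation of the descriptive unsolicited safety profile. Efficacy is not touched.

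**Working it through.** **The plan's own safety figure.** The only quantitative safety statement (protocol 8.5, SAP 2.3) is the probability of seeing at least one event among 1,723 QIVc subjects, 1 − (1 − p)^1723:

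- p = 1/1,000: 82.16% (stated 82.2%)
- p = 1/575: 95.02% (stated 95%)
- p = 1/2,000: 57.76% (stated 57.8%)

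All three reproduce. They concern rare events in the QIVc arm alone and have no bearing on the comparison with the comparator.

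**Which planned tables isolate saline?**

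| Planned output | Separates MenC from saline? |
|---|---|
| Solicited AEs by vaccination 1 / 2 (SAP 4.3) | Yes |
| Unsolicited AEs, treatment period (SAP 6.7.1.3) | No; both doses in two-dose children |
| Unsolicited AEs, follow-up period | No; starts 28 days after the last dose |
| Unsolicited AEs, total period | No; all doses |
| Previously vaccinated subgroup (SAP 6.7.4) | QIVc against MenC only; no saline given |
| Not-previously vaccinated subgroup (SAP 6.7.4) | No; MenC then saline in the same child |

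**How blending acts.** Let q, m and s be the 28-day unsolicited AE risks after one dose of QIVc, MenC and saline, assumed independent between doses. For two-dose children:

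- QIVc, treatment period: 1 − (1 − q)²
- Comparator, treatment period: 1 − (1 − m)(1 − s)
- Difference after dose 2: q − s

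The documents give no rates, so every value below is an assumption.

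*Illustration 1: q = 20%, s = 15%.*

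- QIVc: 1 − 0.80² = 36.0%
- Comparator, m = 25%: 1 − 0.75 × 0.85 = 36.25%; difference −0.25 points
- Comparator, m = 20%: 1 − 0.80 × 0.85 = 32.0%; difference +4.0 points
- After dose 2, either case: 20% against 15%, +5 points (ratio 0.20/0.15 = 1.33)

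*Illustration 2: q = 10%, s = 6%.* The difference after dose 2 is +4.0 points throughout. QIVc over the treatment period is 1 − 0.90² = 19.0%.

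| m | Comparator, treatment period | Difference |
|---|---|---|
| 10% | 1 − 0.90 × 0.94 = 15.4% | +3.6 points |
| 12% | 1 − 0.88 × 0.94 = 17.3% | +1.7 points |
| 14% | 1 − 0.86 × 0.94 = 19.2% | −0.2 points |
| 16% | 1 − 0.84 × 0.94 = 21.0% | −2.0 points |

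If only half of all subjects were on two doses (also an assumption), the all-subject difference would run from 0.5 × 3.6 + 0.5 × (10 − 10) = +1.8 points at m = 10% to 0.5 × (−2.04) + 0.5 × (10 − 16) = −4.0 points at m = 16%.

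The direction is clear. With MenC as reactive as QIVc, most of the excess over saline survives pooling. It vanishes when MenC exceeds QIVc by about as much as QIVc exceeds saline, and reverses beyond that.

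**The case against.** The strongest reply is that the missing line cannot do this work. It is a list of subject subgroups, and every comparator child receives MenC first, so no child belongs to a saline-only subgroup. The protocol's summary of changes records that MenC became the comparator for all subjects. The line may be left over from an earlier design, though that is inference. This stands against restoring the line verbatim. It does not explain dropping it undeclared, and a split by dose interval is a workable way to carry it out.

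A reader might infer that the secondary safety endpoint is not reported as defined, since SAP 3.2 says "Percentage of subjects with any unsolicited AEs will be assessed in the QIVc group and in the comparator group until 28 days after each vaccination". The documents do not support that. Doses are 28 days apart with a window of 0 to +7 days, so the two post-dose windows together nearly fill the treatment period, and the wording does not compel separate percentages. Protocol 8.4.3.1.3 asks for summaries by vaccination group without a dose split, and protocol 8.3.7 leaves time periods to the SAP.

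A reader might also take the interval after dose 2 as a clean randomised comparison of QIVc with saline. It is not. Protocol 4.2 withholds the second dose after severe tolerability problems, so those who receive it are selected after randomisation, and the preceding dose differs by arm.

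Finally, solicited events are already split, the illustrative rates were chosen to show cancellation, and safety has no hypothesis test or success criterion. All of this stands and limits the weight of the point.

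**Conclusion.** The point holds for unsolicited AEs, including related and treatment-period medically-attended AEs, in two-dose children. The SAP omits a protocol-listed safety split without declaring it, and no planned unsolicited table separates saline from MenC. It should not be extended to solicited AEs.

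The size of any masking cannot be computed from the documents. The illustrations rest on assumed per-dose risks and independence between doses. They show that a 4- to 5-point excess over saline can appear as anything from a slightly smaller excess to none or a reversal, depending on MenC. By-subject AE listings would allow a later reconstruction, but that is weaker than a table specified before unblinding. The consequence is descriptive and worth correcting; it does not threaten the trial's primary conclusion.

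**What to change.** Carry out the protocol's comparator split by dose interval rather than by subject. In SAP 6.7.1.3 and 6.7.4, add descriptive tables of unsolicited, related and medically-attended AEs for:

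1. Dose 1 to before dose 2, or to 28 days after dose 1 in one-dose children: QIVc against MenC.
2. Dose 2 to 28 days after it: QIVc against saline, with two-dose children who received dose 2 as the denominator.

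State beneath the second table that its denominator is selected after randomisation and that the preceding dose differs by arm. Keep the pooled treatment-period table. Record in SAP section 7 how the protocol's comparator item has been implemented; if the sponsor decides against the split, section 7 should declare and justify the omission.

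The cost is a short SAP edit and a few extra descriptive tables. The AE onset and vaccination dates are already collected.

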6.8 Interim Analysis

As the circulation of influenza viruses is seasonal and the event rates of influenza are difficult to predict, this study is group sequentially designed to allow for analyses of interim data to enable early study termination when a statistically robust demonstration of efficacy is observed.

An event-driven interim analysis may be performed if deemed necessary by the Sponsor.

In the event an interim is performed, the goal of the interim analysis is to be able to stop the study for early evidence of efficacy. For this analysis a restricted unblinding will be done, i.e. only external Data Monitoring Committee (DMC) members and Contract Research Organization (CRO) employees executing the unblinding receive access to the randomization codes and unblinded data for the purpose of preparing the interim analyses. Interim analyses are only intended to determine if the trial has met criteria for efficacy. Further details regarding the interim analysis are described in the DMC Charter and in Appendix C.

Primary Efficacy Analysis:

Nasopharyngeal swab samples in this study will be analyzed in batches and the number of RT-PCR confirmed influenza cases and its antigenic match to the influenza vaccine strain will be reviewed on a regular basis (blinded review) throughout the study.

An interim analysis for efficacy may be performed, if deemed necessary by the Sponsor:

- If the number of RT-PCR confirmed influenza cases is less or equal to 95 overall, no interim analysis for efficacy will be done and the study will be extended because the probability to make a conclusion for efficacy is too low.
- If the number of RT-PCR confirmed influenza cases is greater or equal to 96 but less than 191, an unblinded interim analysis for efficacy may be performed. To maintain the overall alpha, $\alpha = 1.25\%$ (1-sided), for the hypotheses testing for the primary objectives, an error-spending-function will be used. The benefit of using an error-spending-function is that no maximum number of analysis stages and the timing of the analyses need to be pre-specified, what in practice

Statistical Analysis Plan – Final v2.0

Sponsor Name: Seqirus UK Limited
Sponsor Protocol ID: V130_14

means that the duration of the study in terms of number of seasons can be left open. In this case α -boundaries, forming the adjusted probabilities for the type I error, are calculated using error-spending function and if the p-value for one primary objective is lower than the respective α -boundary the trial stops early (i.e., without reaching the targeted number of cases of 191) for efficacy. Otherwise, the trial continues enrollment. Decisions to stop or continue the trial will be made based on discussions between the DMC and Senior Management.

- If the number of RT-PCR confirmed influenza cases is greater or equal to 191, the study may be unblinded and the final analysis may be performed by the Sponsor. If the trial proceeds to the final analysis (upon reaching 191 cases) the boundaries for acceptance or rejection are identical to the assumed type I and type II errors for the overall design, and the trial stops to either reject or accept the null hypothesis of either one or / and the other of the primary objectives.

In case the DMC states that the observed data provides already the full information level needed for the final test decision, then the final analysis can be done on full alpha level and no further enrollment is needed. However, if the decision of the group-sequential test is to continue the study then it is on the DMC to determine the number of subjects needed to be enrolled. The monitoring committee should not be influenced by the individual results of the study vaccine groups observed at an interim analysis stage when planning further subjects' accrual or the times of future analysis. Only the overall number of cases is allowed to be used for further planning.

The following formula for determination of sample sizes for further enrollment may be used:

$$N_{\text{total}} = (C_{\text{planned}} - C_{\text{observed}}) / [(ER_{QIVc} + ER_{comp})/2],$$

where N_{total} denotes the total number of subjects needed for further enrollment, C_{planned} is the overall number of cases needed for the test, i.e 191 cases, C_{observed} are the at that stage observed number of cases overall, and ER are the respective attack rates assumed for each group. A consideration of early dropout and uncertainty about assumed parameters will be accounted for number of enrolled subjects.

